#### **Exploristics Limited**

### Identifier: EXP20012 Clinical Study Identifier: 132333

reinstating dornase alfa treatment for up to 7 further days (14 days in total). Blood sampling, as specified, will continue until the last day of dosing with dornase alfa.

#### Study controls

Due to the evolving situation with hospitalised COVID-19 participants, the burden on the NHS and the availability of other COVID-19 trials, it is considered inappropriate to conduct a placebocontrolled study. Therefore, a randomised, controlled, open-label approach where dornase alfa is administered on top of BAC and compared to BAC alone has been adopted.

The data derived from the 10 participants who are randomised to the BAC arm of the study who do not receive dornase alfa will provide control data for all of the study endpoints.

Figure 2 Comparator Data. **10** participants Primary endpoints randomised to BAC Secondary endpoints alone Exploratory endpoints 30 participants  $\geq$  60 BAC matched Primary endpoints randomised to BAC historic COVID-19 Secondary endpoints + dornase alpha controls Approximately 10 participants on BAC Exploratory endpoints with bio-banked samples

The 30 participants randomized to BAC + dornase alfa will be compared to 10 randomised controls from the COVASE study. In addition, 10 participants in other clinical trials on BAC (bio-banked samples) and 60 participants from a historic database of the first 120 people with COVID-19 treated at UCLH will also be used as comparator data.

However, to enhance the control group, a hybrid approach will be applied such that additional data will be combined with the randomised controls, illustrated in Figure 2. The sample size calculation indicates that 90 evaluable participants are required (60 control:30 active). These control data may include: data from the randomised BAC arm, historic COVID-19 UCLH database, biobanked samples from other ongoing trials and observational trials in COVID-19. This hybrid strategy allows two things:

- provides comparators for all of the study objectives (including limited data for the exploratory objectives)
- demonstrates that the historic controls are representative/similar to the study population

Comparator data from UCLH is available as historic controls for the Primary and Secondary Endpoints. CRP is routinely measured daily (or on alternate days) in all participants admitted to UCLH and will be used to control for the Primary Endpoint. All of the Secondary Endpoints are also

#### **Exploristics Limited**

# Identifier: EXP20012

Clinical Study Identifier: 132333

routinely measured and will be available in the database. Participants in the database will be selected to act as controls as follows:

- 1. Apply the inclusion and exclusion criteria of the COVASE study
- 2. Additional selection to identify closest matches using a propensity score based on age, gender, BMI, baseline CRP (defined as the last CRP value prior to randomisation, or the first CRP following Dexamethasone for HCs) and whether they have a key comorbidity, defined as one or more of hypertension, diabetes or cardiovascular disease (see Section 11 for details).

At least 60 control participants are expected to be available to act as controls.

Other ongoing and planned trials may be a source of cytokine data as well as biobanked samples that could be used to provide control information on the exploratory endpoints (e.g. ISARIC and RECOVERY Trials) assuming suitable consent is available.

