7.1 Eligibility of trial participants

7.1.1 Trial participant inclusion criteria

1. Male and female participants, aged \geq 18 years

- 2. Participants who are hospitalised for suspected Coronavirus (SARS-CoV)-2 infection confirmed by polymerase chain reaction (PCR) test or radiological confirmation with chest CT
- 3. Participants with stable oxygen saturation (>=94%) on supplementary oxygen
- 4. CRP >= 30 mg/L
- 5. Participants will have given their written informed consent to participate in the study and are able to comply with instructions and nebuliser

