7.1.3 Trial participant exclusion criteria

- 1. Females who are pregnant, planning pregnancy or breastfeeding
- 2. Concurrent and/or recent involvement in other research or use of another experimental investigational medicinal product that is likely to interfere with the study medication within (specify time period e.g. last 3 months) of study enrolment
- 3. Serious condition meeting one of the following:
 - i. Respiratory distress with respiratory rate >=40 breaths/min
 - ii. oxygen saturation<=93% on high-flow oxygen
- 4. Require mechanical invasive or non-invasive ventilation at screening
- 5. Concurrent severe respiratory disease such as asthma, COPD and/or ILD
- 6. Any major disorder that in the opinion of the Investigator would interfere with the evaluation of the results or constitute a health risk for the trial participant
- 7. Terminal disease and life expectancy <12 months without COVID-19
- 8. Known allergies to dornase alfa and excipients
- 9. Participants who are unable to inhale or exhale orally throughout the entire nebulisation period

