#### Figure 1: COVASE Trial Schematic

Participants will be screened, consented, enrolled and randomised up to 3 days after they are admitted to the hospital. They will be randomised in a 3:1 ratio to receive BAC + dornase alfa or BAC alone. A total of 40 participants will be enrolled (30 to receive BAC plus dornase alfa and 10 to receive BAC). On Day1 to Day7 of the trial, participants randomised to the active arm, will receive 2.5mg BID nebulised dornase alfa in addition to BAC. On Day1, Day3, Day5 and Day7, blood samples will be drawn in both trial arms in order to test pharmacodynamic endpoints (PD), biomarkers and clin labs. Clinical assessments will be undertaken daily (as per UCLH clinical guidelines). Participants will be followed until discharge or death or a maximum of 28 days follow-up.

A sample size re-estimation is planned when 12 randomised participants have completed Day7 of follow-up. This analysis will ensure that the assumptions made in the sample size calculation remain valid. However, if the variability is higher than expected then up to an additional 10 participants will be enrolled and treated with dornase alfa (up to 48 participants in total).

CRP has been chosen as the Primary Endpoint because it is a clinically important marker of inflammation and is used to make clinical treatment decisions. In addition, it is induced by the overexuberant inflammation mediated by the NETs and inflammatory histones. CRP is a prognostic marker and correlates with clinical symptoms, inflammation and response to therapy.

Based on clinical judgement, it may be decided to keep some participants on treatment for up to 14 days. In particular, if participants have significant benefits from therapy, but show relapses of the COVID-19 inflammatory state (rising CRP and increasing oxygen requirements in the absence of bacterial infection), on completing 7 days of treatment, then the medical team have the choice of

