#### 5. SAMPLE SIZE CONSIDERATIONS

Sample size calculations were produced using the proc power function in SAS Version 9.4. These were conducted to achieve 80% power to detect a difference in the active arm versus the control group at the 5% level of significance. Based on a mean of 99mg/L in the control group and a common standard deviation of 62mg/L derived from the literature [2, 3], a total sample size of 90 participants would provide sufficient power to detect a greater than a 40% relative difference for CRP in the dornase alfa group compared to the control group. Given the reported average values in severe and non-severe participants and on clinical observations from COVID-19 patients, this difference would be achievable and clinically relevant.

This study will use existing data collected at UCLH from participants admitted with COVID-19 as a comparator group. Participants in the database will be selected to act as controls as follows:

- Apply the inclusion and exclusion criteria of the COVASE study where the appropriate data are available
- Additional selection to identify closest matches

This will give the correct ratio of active versus comparator (ratio of 1:2). To achieve the required power, this would result in 30 participants in the active treatment group and at least 60 in the control. An additional 10 participants will be recruited as a control for the exploratory objectives

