#### **Exploristics Limited**

### Identifier: EXP20012 Clinical Study Identifier: 132333

The following baseline characteristics will be presented:

- Age
- Gender
- Ethnicity
- BMI
- Baseline CRP (defined as the last CRP value prior to randomisation, or the first CRP following Dexamethasone for HCs)
- Whether they have a key comorbidity, defined as one or more of hypertension, diabetes or cardiovascular disease
- White blood cell count
- Neutrophil count
- Lymphocyte count
- Monocyte count
- Eosinophil count
- Basophil count
- Procalcitonin
- D-dimer count
- Ordinal score (WHO scoring tool), using randomized individuals only.
- Last Pre-Dexamethasone CRP (mg/L)
- Days between diagnosis and hospitalization
- Days between hospitalization and baseline
- Days between Dexamethasone initiation and baseline

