#### 11. ANALYSIS CORRESPONDING TO THE STUDY OBJECTIVES

To identify individuals to include in the analysis from the historical controls cohort, the matching procedure will include an initial application of the study inclusion and exclusion criteria to identify the subjects that meet the criteria within the database. Further matching will involve the use of propensity scores to select the controls that most closely match with participants in the active treatment group. The propensity score model will be a logistic regression including all individuals randomised to dornase-alfa and all HCs, with an indicator variable as the outcome to indicate whether the individual is randomised or in the historical control cohort, and covariates included in the model for age, gender, BMI, baseline CRP (defined as the last CRP value prior to randomisation, or the first CRP following Dexamethasone for HCs), and whether they have a key comorbidity, defined as one or more of hypertension, diabetes or cardiovascular disease. The propensity matching will be done using a nearest neighbour approach.

Two controls will be matched for each participant in the active group.

As a supplementary analysis, the propensity score matching will be repeated, but instead of matching on baseline CRP as defined as the last CRP value prior to randomisation, or the first CRP following Dexamethasone for HCs, the matching will be done using the last pre-Dexamethasone CRP measurement, as well as the other factors defined above.

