#### **11.1 Primary endpoint analysis**

#### **Exploristics Limited**

### Identifier: EXP20012 Clinical Study Identifier: 132333

The primary endpoint will be compared between groups using a repeated measures mixed model, adjusted for age, gender, BMI, baseline CRP value (defined as the last CRP measurement prior to randomisation, or the first CRP following Dexamethasone for HCs), time from baseline, and whether they have a key comorbidity, defined as one or more of hypertension, diabetes or cardiovascular disease. An interaction between treatment and time from baseline will also be included in the model. CRP measurements more than 7 days after randomisation (or date of first CRP measurement following Dexamethasone initiation for HCs) will be removed from the analysis, so the comparison is over 7 days.

Due to the treatment by time interaction effect being included in the model, examining the treatment effect alone would be an inappropriate comparison, therefore the least squares means and 95% confidence intervals at the mean follow-up time will be compared between arms, which will take into account both the treatment effect and the treatment by time interaction. These means will be presented on the real scale, e.g. taking the antilog of the least squares mean if the dependent variable has been log-transformed. The difference between the least squares means (on the scale the model was fitted) and the standard error of the difference will be used to generate a treatment z-score, which will be compared against the normal distribution with mean 0 and variance 1, to obtain the two-sided p-value.

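### The 3-day admission-to-randomisation window is not carried into the selection, matching or adjustment of the historical controls

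*SAP*

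**What the plan says.** **Trial patients.** SAP section 3 states: "Participants will be screened, consented, enrolled and randomised up to 3 days after they are admitted to the hospital". Protocol 5.1 says the same.

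**Eligibility lists.** Protocol 7.1.1 has five inclusion items: age, confirmed infection, oxygen saturation, CRP and consent. Protocol 7.1.3 has nine exclusion items. None concerns time since admission, and the protocol summary's criteria add nothing on it. The 3 days in Protocol 8.1 concern the interval between pre-treatment assessments and treatment, not admission.

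**HC selection.** SAP section 3 (Study controls) gives two steps: "Apply the inclusion and exclusion criteria of the COVASE study", then choose the closest matches by propensity score. SAP section 5 has a weaker first step: "Apply the inclusion and exclusion criteria of the COVASE study where the appropriate data are available". SAP section 11 repeats the two-step procedure.

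**Propensity score and model.** The score uses age, gender, BMI, baseline CRP and presence of a key comorbidity. The primary model (SAP 8.2 and 11.1) uses these plus treatment, time from baseline and their interaction.

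**HC time zero.** SAP 11.1 counts the 7 days from randomisation or, for HCs, from the "date of first CRP measurement following Dexamethasone initiation for HCs".

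**Where hospital day appears.** SAP 10.2 lists "Days between hospitalization and baseline" among the baseline characteristics summarised by population.

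**The concern.** A historical comparison depends on both groups starting the clock at a comparable point. Here trial patients have an upper limit on hospital day at entry, and HCs have none. The primary endpoint is CRP over the 7 days after time zero, so where those days fall within the hospital stay affects whether the courses can be compared.

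The SAP's primary comparison pools 60 planned HCs with 10 patients randomised to best available care (BAC), so a mismatch in the HCs would carry most of its weight into the result. Time to discharge and length of hospitalisation are also counted from baseline. The Cox models adjust only for age, baseline CRP and treatment. At the interim, if the HC pool is too small for matching, all HCs enter unmatched, and any mismatch would then feed into the conditional power that decides on extra recruitment.

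**Working it through.** **1. Tracing one HC through the plan.** Take a hypothetical HC whose first CRP after dexamethasone falls on hospital day 8.

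| Step | Is hospital day used? | Result |
|---|---|---|
| Inclusion and exclusion lists (Protocol 7.1.1, 7.1.3) | No | Passes if the other items are met |
| Time zero (SAP 11.1) | No cap | Day 8 becomes baseline |
| Propensity score (SAP 11) | No | Can be matched |
| Primary model (SAP 8.2, 11.1) | No | Not adjusted for |
| Baseline table (SAP 10.2) | Yes, descriptive only | Visible, no consequence |

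A trial patient at the same point would be outside the entry window. HC entry is not free: it is tied to dexamethasone, and SAP section 3 says CRP is measured daily or on alternate days. The gap therefore arises when dexamethasone was started late in the stay.

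**2. The plan's own sample size.** Inputs from SAP section 5: control mean 99 mg/L, SD 62 mg/L, 40% relative difference, 80% power, 5% level, ratio 1:2. SAP 11.1 makes the test two-sided. The difference is 0.40 × 99 = 39.6 mg/L. For a two-sample t-test the noncentrality is 39.6 / [62 × √(1/n₁ + 1/n₂)].

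- 30 against 60: 39.6 / 13.86 = 2.86, power 0.807.
- 29 against 58: power 0.793.

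The stated total of 90 reproduces. The point is not about arithmetic.

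**3. What a mismatch could do (assumed sizes).** The documents do not say how many HCs fall beyond 3 days or how their CRP differs. Suppose mean HC CRP is shifted by b, in either direction, for reasons other than treatment. The pooled comparator shifts by b × 60/70. The standard error for 30 against 70 is 62 × √(1/30 + 1/70) = 13.53 mg/L. With no true effect, the normal approximation gives:

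| Assumed b (mg/L) | Pooled shift | Two-sided false-positive rate |
|---|---|---|
| 0 | 0 | 5% |
| 5 | 4.29 | 6.2% |
| 10 | 8.57 | 9.7% |
| 20 | 17.14 | 24.5% |

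The rate is the same for either sign of b. The sign decides only whether false positives fall mostly for or against dornase alfa. Here b is what remains after matching on and adjusting for baseline CRP.

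**4. Cost of a smaller HC pool (assumed sizes).** Power for 30 dornase alfa patients against the HCs plus 10 randomised controls, with the inputs of step 2:

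| HCs | Controls in total | Power |
|---|---|---|
| 60 | 70 | 0.826 |
| 50 | 60 | 0.807 |
| 40 | 50 | 0.780 |
| 30 | 40 | 0.741 |
| 20 | 30 | 0.682 |

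**The case against.** A reader might infer that the HCs who enter late are deteriorating patients set against fresh admissions, and that the bias favours dornase alfa. The documents do not support either inference.

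- No hospital day is given for any HC, so it is not known that any fall beyond day 3.
- HCs must still satisfy "Participants with stable oxygen saturation (>=94%) on supplementary oxygen" and CRP of at least 30 mg/L, and must not fall under "Require mechanical invasive or non-invasive ventilation at screening", at least where data exist. They are matched on baseline CRP and the model adjusts for it. A stable, unventilated patient late in the stay could be recovering, which would work against the drug.
- Needing dexamethasone does not in itself separate the groups. SAP 6.2 treats starting dornase alfa before dexamethasone as an important protocol violation, so dexamethasone is expected in trial patients too.

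The SAP also plans checks: the hospital-day table, a randomised-only comparison, a comparison of randomised BAC patients with HCs (SAP 8.3.1), and a rematch on pre-dexamethasone CRP (SAP 11). They deserve credit, but none uses hospital day to select, match or adjust. The two SAP 8.3.1 comparisons rest on about 10 randomised controls. The SAP plans no formal test between the primary and additional treatment estimates, and says only that substantial differences will be noted. These checks may reveal a mismatch but leave the primary estimate as it is.

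A strict 3-day exclusion with no fallback would also conflict with two controls per active patient (SAP 11) and with the 60 HCs planned (SAP 12). That part of the objection stands, and it shapes the fix.

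**Conclusion.** The gap holds as a matter of text. The 3-day window applies to trial patients, is never applied to HCs, and is not replaced by any matching or model covariate. It affects up to 60 of the 70 comparators (86%) in the pooled primary analysis, and the secondary analyses that use HCs.

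The size and direction of any resulting bias cannot be determined from the documents. The false-positive rates of 6% to 24% are illustrations. They rest on assumed HC shifts of 5 to 20 mg/L, the planning SD of 62 mg/L and a simple two-group comparison instead of the repeated-measures model. If all HCs happened to fall within 3 days, the omission would have no effect. This should be corrected, because the plan does not ensure that condition and the needed variable is already to be tabulated.

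**What to change.** In SAP sections 3, 5 and 11, add a selection rule applied before propensity matching: an HC is eligible only if the index date (the first CRP after dexamethasone) is no more than 3 days after admission, with the eligibility criteria assessed at that date where data are available.

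State the fallback in advance. If too few HCs remain for 2:1 matching, add days from admission to baseline to both the propensity score and the primary model, and report a sensitivity analysis restricted to HCs within 3 days. Keep the hospital-day row in the baseline table in either case.

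**Cost.** The change is to SAP wording and uses a variable the SAP already plans to tabulate. The strict rule may shrink the HC pool and lose precision: under the planning assumptions, power is about 0.74 with 30 HCs against 0.83 with 60. The fallback costs one more covariate, and relies on that covariate to handle HCs at hospital days where there are no trial patients. The restricted sensitivity analysis is there to check this.

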### 4. PLANNED ANALYSES

There are two planned analyses, an interim analysis after 12 randomised individuals have completed Day7 follow-up and the final analysis, once all randomised individuals have completed follow-up (which is the minimum of discharge, death or 35 days after randomisation). At the interim analysis, only the primary endpoint and safety data will be examined, and no secondary or exploratory endpoints. A promising zones approach [1] (see Section 12 for details) will be followed at the interim analysis stage to identify the conditional power and make a decision as to whether to continue enrolment up to the planned 40 individuals randomised, or whether to increase the planned sample size up to a maximum of 48 randomised individuals. See Section 12 for details.

After the final randomised participant has completed follow-up, a more complete analysis will be undertaken, including examination of endpoints relating to the primary, secondary and exploratory objectives. A full safety analysis will also be carried out at this stage.

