- Ventilator-associated pneumonia (VAP) or hospital-acquired pneumonia

• Survival (days)

In participants who are discharged before Day35, a telephone call will occur at Day35 to ask them about their breathing e.g. Are you short of breath? Has your breathing returned to the same level as previously?

A schedule of all trial assessments and procedures is set out in Appendix 1.

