- Clinical Laboratory assessments include: glutamate pyruvate transaminase (GPT / ALAT), glutamicoxaloacetic transaminase (GOT / ASAT), gamma-glutamyl transferase (gamma-GT), alkaline phosphatase, total bilirubin, creatinine, chloride, potassium, sodium, total protein, albumin, Lactate, Renal function: (Creatinine, Urea and Na, K, Cl), Clotting screen including Prothrombin time, Bone profile (ca2+), High-sensitivity troponin, Ferritin, LDH, Creatinine
- 3. CRP, PCT and D-Dimer are measured in the clinical laboratory sample
- Full Blood Count: leukocytes, erythrocytes, haemoglobin, haematocrit, mean corpuscular volume (MCV), mean corpuscular haemoglobin (MCH), platelets, neutrophils, eosinophils, basophils, lymphocytes, monocytes
- 5. Pharmacodynamics: may include but is not limited to Cell-free DNA (cfDNA), Circulating histone, Citrullinated H3, NET Elisa assay
- Biomarkers: may include but is not limited to Circulating pro-inflammatory cytokines (e.g. IL-6, TNFα, IL-1β, IL-8), Markers of activation of the coagulation (e.g. fibrin, tissue factor, Von Willebrand factor,

thrombin, thromboxane A2) and complement cascade (e.g. C1q), haemolysis (e.g. red blood cell lysis), NET formation

- 7. Bronchial secretions will be collected as appropriate for clinical reasons only (e.g. spontaneous expectorant or bronchoscopy during MV)
- 8. Dornase alfa administered daily at 2.5mg BID by nebuliser
- 9. In participants who are discharged prior to Day35, a follow-up telephone call will take place to ask about their breathing.
- 10. In participants who receive dornase alfa (2.5mg BID) beyond Day7, additional blood draws and procedures will take place on Day9, Day11, Day14
- 11. Final study visit is at discharge or Day35 whichever comes first
- 12. Adverse events will be recorded every day and not just on study visit days

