#### 2.2.2 Secondary Endpoints

Secondary endpoints include, but are not limited to:

- Levels of acute phase reactant CRP over 35 days follow-up
- Length of hospitalisation from baseline (days)
- Survival at Day35, mortality data collected from EPIC database for both HCs and randomised individuals
- White blood cell count over 7 days follow-up
- Neutrophil count over 7 days follow-up
- Lymphocyte count over 7 days follow-up
- Monocyte count over 7 days follow-up
- Eosinophil count over 7 days follow-up
- Basophil count over 7 days follow-up
- Procalcitonin over 7 days follow-up
- D-dimer count over 7 days follow-up
- Blood pressure over 7 days follow-up
- Pulse rate over 7 days follow-up
- Temperature over 7 days follow-up
- Respiratory rate over 7 days follow-up
- Time on Oxygen over 7 days follow-up
- Time on Oxygen over 35 days follow-up
- Proportion of individuals with Pneumonia over 7 days follow-up
- Ordinal score (WHO scoring tool) over 7 days follow-up (including randomized individuals only)
- Proportion of individuals on Mechanical Ventilation (MV) over 7 days follow-up
- Time on MV over 7 days follow-up
- Length of ICU stay (hours) over 7 days follow-up
- Proportion of individuals with Pneumonia over 35 days follow-up
- Proportion of individuals on Mechanical Ventilation (MV) over 35 days follow-up
- Time on MV over 35 days follow-up
- Length of ICU stay (hours) over 35 days follow-up

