For the following secondary endpoints, a survival analysis will be conducted. The number of events by arm will be compared. The time to event data will be censored at 28 days post last dose (Day35) for the randomised participants and at 35 days after baseline, or the date of the last electronic record, whichever is earlier, for the historical control group. If median time-to-event times exist, the Kaplan-Meier method will be used to estimate the median time-to-event times and the associated 95% confidence intervals. The survival model will include treatment as a stratification variable and significance assessed using a log-rank test. A Cox proportional hazards model will be used to generate a hazard ratio and associated confidence intervals, adjusting for age, baseline CRP value (defined as the last CRP measurement prior to randomisation, or the first CRP following Dexamethasone for HCs) and treatment as a main effect. For the time to discharge from hospital analysis, data will be censored if the participant dies prior to discharge at the date of death.

- Survival at Day35
- Time to discharge from hospital from baseline (days) to Day 35

For the following secondary endpoint, a logistic regression model will be fitted, with age, gender, BMI baseline CRP value (defined as the last CRP measurement prior to randomisation, or the first CRP

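### The final analysis may begin once the last inpatient is discharged, yet randomised participants are credited with survival to Day 35 without the last-record limit applied to historical controls

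*SAP*

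**What the plan says.** **Timing.** SAP section 4 places the final analysis "once all randomised individuals have completed follow-up (which is the minimum of discharge, death or 35 days after randomisation"). The same section adds that "After the final randomised participant has completed follow-up, a more complete analysis will be undertaken", covering primary, secondary and exploratory endpoints and full safety. Discharge therefore completes follow-up for this purpose. Protocol Appendix 1, note 11, agrees: "Final study visit is at discharge or Day35 whichever comes first". Protocol 8.11 ends the trial at the last participant's last visit.

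**Endpoint.** SAP 2.2.2 lists "Survival at Day35, mortality data collected from EPIC database for both HCs and randomised individuals".

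**Censoring.** SAP 11.2 states: "The time to event data will be censored at 28 days post last dose (Day35) for the randomised participants". For the comparators it uses 35 days after baseline, "or the date of the last electronic record, whichever is earlier, for the historical control group". Only the historical group has a limit tied to what was recorded.

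**Contact after discharge.** Protocol 8.4.1 provides: "In participants who are discharged before Day35, a telephone call will occur at Day35". The example questions concern breathing.

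**Other wording on length of follow-up.** SAP section 3, like Protocol 5.1, says: "Participants will be followed until discharge or death or a maximum of 28 days follow-up".

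**The concern.** The event that releases the final analysis and the horizon of the survival endpoint are different dates. A participant discharged on Day 8 has completed follow-up under SAP section 4, but SAP 11.2 gives that participant 35 days of survival time unless a death is on record. Days that have not elapsed at the data cut, or that nobody has verified, would enter the risk set as event-free.

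The groups are not exposed equally. SAP 11.2 runs the secondary analyses in the primary analysis population, which SAP 6.1 defines as both randomised arms plus matched historical controls. All 30 dornase alfa participants fall under the fixed Day 35 rule. Among the comparators only the 10 randomised to BAC do; the 60 historical controls leave the risk set at their last record if that is earlier. A death after the cut would be missed, and person-time overstated, mostly on the dornase alfa side of a planned log-rank test and Cox model.

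**Working it through.** **1. The plan's own figure.** Day 35 as 28 days after the last dose: 7 + 28 = 35, which reproduces for 7-day dosing. For the permitted 14-day course the same phrase gives 14 + 28 = 42. For BAC participants there is no last dose, so it is undefined.

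**2. Who falls under the fixed rule (SAP section 12, planned numbers).** Dornase alfa: 30 of 30. Comparators: 10 of 10 + 60 = 70, or 14%.

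**3. How much time could be unobserved.** Inputs:
- Randomised participants: 40 (SAP section 3). Planned person-days: 40 × 35 = 1,400.
- Recruitment rate r: 3 to 6 a week (Protocol 7.2); Protocol 11.2.2 gives 3 to 5.
- Day d of the last recruit's discharge: not in the documents. Assumed 8 to 12, taking the last recruit as the last to leave hospital.

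With even recruitment, the participant randomised k places before the last has u(k) = 35 − d − 7k/r days not yet elapsed at the trigger, counted only when positive.

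- r = 3, d = 12: u(k) = 23 − 2.333k, positive for k = 0 to 9, so 10 participants. Sum = 10 × 23 − 2.333 × 45 = 230 − 105 = 125 days; 125/1,400 = 8.9%.
- r = 6, d = 8: u(k) = 27 − 1.167k, positive for k = 0 to 23, so 24 participants. Sum = 24 × 27 − 1.167 × 276 = 648 − 322 = 326 days; 326/1,400 = 23.3%.

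The same formula over a wider range of d:

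| Last discharge (d) | r = 3 | r = 5 | r = 6 |
|---|---|---|---|
| Day 8 | 12 people, 12.1% | 20, 19.6% | 24, 23.3% |
| Day 12 | 10, 8.9% | 17, 14.3% | 20, 17.0% |
| Day 14 | 9, 7.5% | 15, 12.0% | 18, 14.2% |
| Day 28 | 3, 1.0% | 5, 1.5% | 6, 1.8% |

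**4. Why these are upper-end values.** The trigger is the latest discharge among all 40, so one long stay near the end of recruitment delays it for everyone, and participants who have already died contribute no unelapsed days. With stays simulated for all 40 (assumed lognormal, median 8 days, log-SD 0.7, capped at 35), the average is about 8 participants and 7% of person-days at 3 a week, and about 13 participants and 9% at 6 a week. If the last recruit stays to Day 35, or the extract is taken five weeks after the last randomisation, the number is zero.

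**5. What the other provisions secure.** EPIC cannot hold deaths on days that have not occurred at extraction. The Day 35 call could establish vital status, but SAP section 4 does not wait for it and its stated content is breathing. Neither is linked to the date of the data cut.

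**6. Which analyses are affected.** The primary endpoint stops at 7 days. In the time-to-discharge analysis everyone has been discharged, has died or has reached Day 35 at the trigger, so it is complete. Survival is the analysis exposed. The other 35-day endpoints share the trigger and could miss events after a readmission.

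**The case against.** The strongest reply is that SAP section 4 sets an earliest point, not a data cut. The effective SAP is dated 12 August 2021, and its July and August revisions already describe what the trial and historical data contain, so the extract may well postdate Day 35 for everyone. The protocol synopsis allows six weeks from consent to last assessment, mortality comes from EPIC for both groups, and a Day 35 call is planned. All of this stands. A reader might infer that the analysis did, or must, start at the last discharge; the documents do not say so. What remains is that no rule requires the wait.

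The size can also be challenged. Six recruits a week sits poorly with 12 to 15 weeks for 40 participants, which is 40/15 to 40/12, or 2.7 to 3.3 a week. That stands, and it favours the left-hand column of the table.

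A reader might go further and say that deaths are missed only in the dornase alfa arm, or that a lost death is likely. Neither is supported. Randomised BAC participants share the rule, and historical controls may themselves be observed for less than 35 days. The Protocol section 3 mortality of 4% to 15% would give 1.2 to 4.5 deaths among 30, so a single death would carry weight. But that figure is for COVID-19 pneumonia overall; the documents give none for deaths between discharge and Day 35.

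Finally, the 28-day maximum looks like a rival end of follow-up. It follows the description of Day 1 to Day 7 dosing and can be read as 28 days after it, which is Day 35. It is a matter of clarity more than a proven contradiction.

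**Conclusion.** The concern holds as a gap in the rules. Followed literally, SAP sections 4 and 11.2 allow unelapsed or unverified days to count as survived for every dornase alfa participant but for only about one comparator in seven. The tendency is to favour dornase alfa in the Day 35 survival comparison.

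The extent is conditional. With the last discharge at Day 8 to 12 and 3 to 6 recruits a week, at most about 10 to 24 of 40 participants (25% to 60%) and 9% to 23% of person-days are affected. Longer stays or a later extract reduce this, possibly to none. These percentages are ceilings under assumed discharge days and should not be read as expected values. The effect on the hazard ratio cannot be sized from the documents.

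The primary result is not at risk. Survival is an unpowered secondary endpoint, though one with a planned test and hazard ratio. The correction is worth making because it is cheap and removes a one-sided rule.

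**What to change.** - **SAP section 4:** run the Day 35 survival analysis only after every randomised participant has died or reached Day 35, using a vital-status extract dated on or after the day the last of them does. If the extract already meets this, a sentence giving its date closes the point.
- **SAP 11.2:** censor both groups at the earlier of 35 days after baseline and the date last known alive. The common rule needs the extract alongside it; otherwise many participants would simply be censored at discharge.
- **Wording:** reconcile the 28-day maximum (SAP section 3, Protocol 5.1) and the definition counted from the last dose (SAP 11.2, Protocol 11.3.3) with that single horizon measured from baseline. It then applies equally to participants with extended dosing and to those on BAC alone.
- **Day 35 call:** record vital status as well as breathing.

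The cost is wording plus a wait of 35 − d days after the last discharge: 23 to 27 days for d = 12 to 8, so at most about four weeks. The Day 35 contact is already planned.
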